### 1.1 Specific Aims

- A. Compare the effectiveness, safety, and cost of two treatments for moderate to severe FI in 194 male and female patients in a multi-center RCT; the interventions are biofeedback therapy (5 required weekly sessions with the option of an additional 6th visit, as needed) and perianal injection of the inert bulking agent dextranomer (INJ; Solesta). A ≥75% reduction in average weekly FI episodes compared to baseline will define a responder. The primary efficacy analysis will occur 3 months following the start of each treatment, with long-term follow-up through 2 years. Secondary outcomes will include a validated FI severity scale, a disease-specific quality of life scale, and measures of psychological distress.
  - Research objective 1 (primary). For the primary test of efficacy, the null hypothesis is that the proportion of responders in the two treatment groups will not be different. Secondary analyses will test for equivalence at other time points (e.g., 6, 12 and 24 months follow up) and will compare treatment groups on other secondary outcome measures.
  - Research objective 2 (primary). For the primary test of safety, the null hypothesis is that at 3 months follow up, the proportion of patients with adverse events (AEs) of pelvic pain of grade II or higher based on Common Terminology Criteria for AE (CTCAE) criteria, treatment site infection, or SAEs requiring hospitalization will not be different in the BIO or INJ groups. Secondary analyses will evaluate this outcome at 6, 12, 18, and 24 months follow up.
  - Research objective 3 (primary). At 3 months follow up, the estimated average cost for enhanced medical management non-responders will not be different for the two treatments. Secondary analyses will evaluate this outcome at 6, 12, 18, and 24 months.
- B. Compare efficacy in patients who complete all assigned treatment visits. Efficacy may be influenced by the number of BIO treatment sessions and the requirements to learn and practice new skills. Thus, in a secondary analysis, the primary efficacy outcome will be compared between treatment groups in the subset of participants who completed the treatment to which they were randomized.

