Graf reported there were 128 adverse events and two serious adverse events (AEs) in the 136 patients who received INJ. However, many of these were minor AEs related to changes in stool consistency. The incidence of more significant AEs, such as pain, fever, and/or abscess, was 9.6%. Other investigators have reported comparable rates of AEs in uncontrolled case series. Dextranomer treatment is not consistently reimbursed by third party payers but is estimated to cost approximately \$7,408 if two injections are given

2.2.3. Sacral Nerve Stimulation: SNS is performed in two steps: (1) During test stimulation, a temporary electrode is inserted with its tip near the sacral nerve and connected to an external stimulator for 1-2 weeks. However, screening procedures are evolving, with many surgeons now preferring to use barbed leads intended for permanent implant during the screening stage, reasoning that 70% to 90% of patients will improve enough to warrant a permanent implant, and for these patients, the permanent lead is already in place. In this study, we plan to use the tined lead to avoid the need for a second test if the PNE fails. (2) If FI frequency decreases by at least 50% during PNE, a battery-operated electrical stimulator is permanently implanted beneath the skin. An estimated 10% - 30% of patients fail to meet criteria for permanent implant. Publications on the effectiveness of SNS often report only the outcomes for patients receiving permanent implants, but this makes these outcomes not comparable to reports on BIO and INJ where the analysis sample includes all patients randomized to treatment (intent-to-treat analysis). Consequently, in the literature review below, we adjust for the number of patients failing test stimulation and report the intention-to-treat (ITT) outcomes for SNS.

Although SNS is regarded as standard of care for patients with severe FI who have failed enhanced medical treatment and is approved by the FDA for this indication, few RCTs have been published. Wexner reported a large, uncontrolled multisite study, and this carefully done study was used for our sample size calculations. This study included 133 patients with at least two episodes of solid or liquid FI per week at baseline. After correction for patients who failed the test stimulation, the proportion achieving a 50% reduction by ITT analysis was 71.4% at six months and 66.2% at 12 months.

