	Allergy to hyaluronic acid-based products
	Active anorectal conditions in the last 6 months including abscess, fissures, sepsis, significant bleeding, proctitis, colovaginal and rectovaginal fistulas, anorectal tumors, or other infections.
	If the patient's physician believes it is unsafe for the patient to temporarily stop anticoagulants for any test procedures and treatments associated with the study.
	Patients who have 4 or more days with 4 or more bowel movements classed as a 6 or 7 on the Bristol Stool Scale per day in either (any) week during the Baseline will be excluded.
	Patients with Parkinson's disease, multiple sclerosis, severe diabetic neuropathy documented by EMG, and neurodegenerative disorder.
	Patients currently receiving immunotherapy or chemotherapy
	Significant anal pain in the last 6 months.
	If the patient is unwilling to stop using over-the-counter medications, herbal supplements, or prescribed medications for the purpose of modifying stool consistency, that are not included in the approved medications list (loperamide, laxatives, fiber supplements, and Questran are approved medications), for the duration of the research study.

Medical history will be documented to test for predictors of response.

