#### Table 3: Preliminary Data for Sample Size Calculations

#### Table 4: Preliminary Data on Other Outcome Measures

Outcome Measure	BIO Heymen 	INJ Graf 	Sample size required per group
 Adverse events (% subjects)	0%	9.6%	74
 Estimated cost (\$)	\$1,435	\$7,408	
 % Change in quality of life impact	11.9% (SD = 21.5)	27.3%	32
 St Mark's Score or FISI, Average % decrease	36% (SD = 45.8)	17.9%	102

There were 128 AEs in 136 patients, but some were relatively minor. We list only the estimated rate of pain, fever, and abscess (13 events in 136 patients). Sample size calculations are for tests of proportions with alpha = .05 and beta = .80. Costs are estimated from published Medicare reimbursement tables are not compared statistically.

Continuous outcomes for quality of life and FI severity calculations assume alpha = .05 and beta = .80.

It is anticipated that up to 15% of participants enrolled in the study will drop out (with no further follow up). before completing enhanced medical treatment. If the number who drop out exceeds 15%, additional subject will be recruited and enrolled into the study, but prior research suggests that 15% is a reasonable estimate. Another 15-20% are expected to achieve a 75% reduction in FI during EMM and will need to be replaced Thus,

we anticipate that approximately 285 participants will need to begin EMM treatment in order for 194 to complete the run-in phase and be randomized to BIO or INJ (97 per group). The participant flow diagram is shown in Figure 3.

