#### 5.2.2. Primary Safety Outcome

For the primary safety outcome, we will use Fisher's exact tests to compare the percentage of participants in the two randomized treatment groups who experience an adverse event (AE) of pelvic pain of grade II or greater severity, treatment site infection, or a serious adverse event (SAE) requiring hospitalization between randomization and the 3-month assessment. For this analysis, participants who are missing safety data will be excluded from analysis, but we assume that 78 in the BIO group and 92 in the INJ group will be available for evaluation at 3 months and that those numbers represent the minimum number of participants who will be included in the primary safety analysis. Based on previous studies, we expect the percentages of participants with a qualifying AE or SAE to be approximately 9.8% (9/92) in the INJ group, and 0% (0/78) in the BIO group. The anticipated sample size will provide 83% power to detect a pairwise difference between percentages of 0 and 10% at an alpha of 0.05.

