*6.3 INJ of dextranomer:* This protocol is a modified version of the protocol used by Graf to ensure consistency across sites and safety of patients. Patients are treated prophylactically with oral antibiotics to minimize injection site infections. One ml of NASHA dextranomer is injected through an anoscope into each quadrant of the submucosa (4 ml total) approximately 5 mm above the dentate line. After each INJ, the needle is left in place for 10 seconds to avoid backward leakage of contrast through the injection channel. Following the INJ patients are counselled to use stool softeners (docusate sodium) until the first bowel movement and to use paracetamol as needed for INJ site discomfort. Prophylactic antibiotics will be administered for 2 days starting on the day of injection. Six weeks after initial INJ, patients return for evaluation, and if the patient has achieved less than 75% reduction in FI, a second INJ is given.

6.4 Comparison of elements of BIO and INJ:

Table 9 shows the elements of the two treatments compared to each	h other.
	rouior.

	Enhanced Medical Management	Biofeedback	Injection
Preparation	None	None	Diet restrictions; enemas; and antibiotics per the procedure SOP
Number of visits	2 visit + 2 phone calls	5-6 visits	2 visits
Visit duration	60 min 1 st visit; 15 min phone calls (Day 3; Day 14); 30 min last visit	60 min	45 min
Visit frequency	1 st and last visits (start of treatment and after treatment program has ended)	Up to 2 visits per week, spaced 2-10 days apart for first 5-6 weeks or so	0 and 6 weeks
Procedure	Daily sphincter exercises, meds to normalize bowel habits	Learn how to improve strength and rectal sensation	Bulking agent injected into rectal wall to narrow opening
Expected Adverse Events	None	None	Pain at injection site, bleeding, infection

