## 8.0 Statistical Considerations

## 8.1 Analysis of Primary Endpoints

Assessment of Randomized Treatment Response at 3 Months (Primary Efficacy Analysis). To test the efficacy of randomized treatment assignment, a generalized linear model with a logit link will be constructed to predict treatment response at 3 months post-randomization. Treatment group and the stratification factors of clinical site and sex will be included in the model as categorical independent variables. An ITT approach will be used in which participants will be analyzed based on their assigned treatment group regardless of actual treatment received. Participants without a valid bowel diary at 3 months due to drop out or other reasons will be classified as non-responders. Using this model, we will test the null hypothesis that the proportion of responders is the same in the two treatment groups at 3 months following randomization using an alpha of 0.05. Sensitivity analyses will be conducted to assess the impact of classifying participants with missing data as non-responders.

Assessment of Safety. The primary safety outcome is the percentage of participants in each randomized treatment group who experience an adverse event (AE) of pelvic pain of grade II or greater severity, treatment site infection, or a serious adverse event (SAE) requiring hospitalization between randomization and the 3 month assessment. Because the proportion of participants with one of these events is expected to be small, Fisher's exact tests will be used to compare the percentage of participants with a qualifying adverse event. The difference between the two treatment groups will be evaluated for significance using an alpha of 0.05. Participants who are missing safety data due to drop out or other reasons will be excluded from this analysis.

*Cost of Care Analysis.* Mean and median costs per participant will be estimated for each of the two treatment groups and from the perspectives of payers, patients, and society. We will analyze whether differences in costs through 3-month follow up across the intervention arms and perspectives are statistically significant using parametric t-tests or using non-parametric bootstrapping methods. We will evaluate differences between the two treatment groups using an alpha of <0.05.

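### The primary safety composite names pelvic pain only, does not say whether injection-site pain counts, and is powered on a rate with a different definition

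*Combined protocol and SAP*

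**What the plan says.** Section 4.1 names three primary outcomes: efficacy, safety and cost. Section 1.1, objective 2, defines the safety outcome as "pelvic pain of grade II or higher based on Common Terminology Criteria for AE (CTCAE) criteria, treatment site infection, or SAEs requiring hospitalization". Sections 5.2.2 and 8.1 repeat this three-part composite for the period from randomization to 3 months, in Section 8.1 as "an adverse event (AE) of pelvic pain of grade II or greater severity, treatment site infection, or a serious adverse event (SAE) requiring hospitalization", and Section 8.2 carries it to 24 months. Section 8.1 compares the arms with Fisher's exact test at alpha 0.05.

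Table 9 (Section 6.4) lists the adverse events expected with INJ as "Pain at injection site, bleeding, infection" and expects none with BIO. Section 6.3 anticipates discomfort at the injection site and puts the injection about 5 mm above the dentate line. Elsewhere the protocol has a separate term for pain at this location: an exclusion criterion in Section 5.1 reads "Significant anal pain in the last 6 months".

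For planning, Section 5.2.2 expects qualifying events in "approximately 9.8% (9/92) in the INJ group, and 0% (0/78) in the BIO group", citing previous studies without naming them, and states 83% power for 0% against 10%. The only matching figure is from the sham-controlled dextranomer trial. Section 2.2.2 says of it: "The incidence of more significant AEs, such as pain, fever, and/or abscess, was 9.6" (per cent). Footnote 1 to Table 4 explains: "We list only the estimated rate of pain, fever, and abscess (13 events in 136 patients".

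**The concern.** There are two separate mismatches.

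The first is between the endpoint and the expected harm. If a site records grade II pain as anal, rectal or injection-site pain, a literal reading leaves it out of the composite. If another site records the same complaint as pelvic pain, it counts. Only INJ has an injection site, so narrow coding would remove mainly INJ events and shrink the difference. Staff are unmasked (Section 7.2.2). The masking described in Section 7.2.3 covers diary and questionnaire outcomes, and the Medical Safety Monitor's review in Section 4.1.2 concerns relatedness and expedited reporting. No masked classification of events into the composite is described.

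The second is between the endpoint and its planning rate. Section 5.2.2 treats 9.8% as the rate of the endpoint as defined, but the apparent source has other components, another unit of count and no stated grade threshold. The power statement therefore describes a quantity that the trial will not measure.

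**Working it through.** **Definitions side by side**

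| | Primary composite (8.1) | Expected INJ events (Table 9) | Apparent source of planning rate (Table 4, footnote 1) |
|---|---|---|---|
| Pain | Pelvic, grade II or worse | At injection site | Pain, no location or grade stated |
| Infection | Treatment site infection | Infection | Abscess |
| Bleeding | Only through a hospitalized SAE | Yes | Not listed |
| Fever | Only through infection or a hospitalized SAE | Not listed | Yes |
| Hospitalized SAE | Yes, any cause | Not listed | Not listed |
| Unit | Participants | – | Events |

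Table 1 rounds the same trial's rate to 10% and labels it pain or infection, which is a third description.

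**Source of 9.8%.** 13/136 = 9.56%. Applied to 92 participants, 0.0956 × 92 = 8.8, rounded to 9, and 9/92 = 9.8%. The link is an inference from the figures, but no other figure in the documents fits.

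**The plan's power figure.** Inputs from Section 5.2.2: n = 78 (BIO) and 92 (INJ), p = 0 and 0.10, alpha 0.05, taken as two-sided. The pooled normal approximation is

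power = Φ{[p₂ − 1.96·√(p̄(1−p̄)(1/78+1/92))] / √(p₂(1−p₂)/92)}.

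With p₂ = 0.10, p̄ = 9.2/170 = 0.0541. The null standard error is 0.0348 and the alternative standard error is 0.0313, so power = Φ[(0.1000 − 0.0683)/0.0313] = Φ(1.015) = 84.5%. At p₂ = 9/92 it is 83.6%. The stated 83% is reproduced to within 2 points.

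**Power of the planned Fisher test.** With a BIO rate of 0%, the BIO count is always 0. The two-sided p-value is 0.063 for 5 INJ participants with an event and 0.032 for 6, so at least 6 are needed. Power is P(X ≥ 6) with X ~ Binomial(92, p). At p = 0.10 this is 90.8%, and at 9/92 it is 89.6%.

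**Sensitivity.** Let k be the number of the 13 source events that would meet the composite, with one event per participant and an INJ rate of k/136. The value of k is an assumption.

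| k of 13 | INJ rate | Fisher power |
|---|---|---|
| 13 | 9.6% | 88% |
| 12 | 8.8% | 83% |
| 11 | 8.1% | 76% |
| 10 | 7.4% | 68% |
| 8 | 5.9% | 46% |
| 6 | 4.4% | 22% |

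Power is 80% at an INJ rate of about 8.5% and 50% at about 6.2%. Losing two of the 13 events is enough to fall below 80%.

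**The case against.** The composite does not count pelvic pain alone, though a reader might infer that from its pain term. Treatment site infection and hospitalized SAEs also qualify, an injection-site abscess would reasonably count as infection, and infection is itself one of the three expected INJ events in Table 9. This stands, and it confines the gap to non-hospitalized local pain that is not classed as pelvic, plus bleeding and isolated fever.

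Pelvic pain can be read as a regional term that covers anal and injection-site pain, and nothing in the protocol forbids that. The anal pain wording in Section 5.1 is an eligibility item, not an adverse event category. Case report forms and operating procedures are separate documents and may hold a mapping rule. This also stands: the protocol shows an ambiguity, and a biased comparison would follow only from how sites code.

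BIO uses catheters and rectal balloon distension, so local pain is not exclusive to INJ. That is fair, although Table 9 expects no BIO events.

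All adverse events are recorded to 3 months (Section 9.2), specific events will be compared at the end (Section 4.1.2), and the DSMB sees comparisons of event rates (Section 8.4). The data are therefore not lost. These comparisons do not settle what the primary outcome counts, and the Section 8.1 test is the only safety comparison with a set alpha.

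Finally, the source events were described as more significant ones after minor events were set aside, which argues against a large share below grade II. That is reasonable but cannot be checked, because no grades are given.

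**Conclusion.** Both mismatches are real and should be resolved before analysis. The protocol does not say whether the pain it expects from INJ qualifies for the pain component of a primary outcome. Read literally, the composite can leave that pain out, mainly in one arm. The 9.8% planning rate is not on the endpoint's definition, whichever way sites code pain.

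The size cannot be fixed from the documents. Fisher power runs from about 90% at 9.8% to below 80% under about 8.5%, and to about 46% at 5.9% (8 of 13 events qualifying). This assumes a two-sided test, 92 and 78 evaluable, no BIO events, and 13/136 as the source.

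Three stronger readings are not supported:
- That INJ harm will be under-counted. This depends on coding that the documents do not describe.
- That the safety comparison is underpowered. At the stated rate the planned test has more power than the 83% claimed.
- That 9.8% is an upper bound, or that the source events were of any grade. No grade is stated. Counting events rather than patients, including fever and omitting a grade cut could make the endpoint's rate lower, but SAEs requiring hospitalization count without a relatedness condition and could make it higher.

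**What to change.** Before analysis, in Section 1.1 objective 2 and Sections 5.2.2, 8.1 and 8.2, define the pain component as *pelvic, anal, rectal or injection-site pain of CTCAE grade II or higher*. Apply it identically in both arms and list the qualifying terms on the adverse event form. Make the same change in objective 7, which uses the pelvic pain term for the medical management phase, so that the definitions agree.

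In Section 5.2.2, state that the planning rate comes from 13 events of pain, fever and abscess in 136 patients with no stated grade cut, and that the participant-level rate of the endpoint as defined may differ. Give power over a range of INJ rates, for example the table above.

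No new data are needed: all adverse events are already recorded to 3 months, with CTCAE grading. There are two costs. A primary endpoint definition is amended during an unmasked trial, so the change should be dated and made without reference to event counts by arm. Some post-treatment soreness rated grade II will also count in either arm. BIO events would lower power: with INJ held at 10%, a BIO rate of 1% takes Fisher power from 91% to 74%.

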#### 8.2 Analysis of Secondary Efficacy Endpoints

Assessment of Efficacy through 24 months. Treatment response (≥75% reduction in weekly FI episodes) at time points through 24 months will be analyzed using a longitudinal extension of the model used for the primary efficacy analysis. Month of assessment, and interaction between month and other predictors, will be included in the model, and the correlation between measures assessed on the same participant over time will be modeled using an appropriate covariance structure. Participants classified as non-responders at 3 months will continue to be considered non-responders at subsequent time points. Participants with missing responses will be classified as non-responders, but sensitivity analyses will be conducted to assess the impact of this assumption.

Assessment of Safety through 24 months. The percentage of participants reporting AEs of pelvic pain of grade II or greater severity, treatment site infection, or an SAE requiring hospitalization by 6, 12, 18, and 24 months will be estimated with 95% confidence intervals using the Wilson Score interval method. Separate estimates will be produced for the groups of participants treated with each of the two therapies alone, and for participants in each of the treatment-order combinations. Confidence intervals will be compared descriptively.

Assessment of Cost of Care through 24 months. The median costs per participant from the perspectives of payers, patients, and society through 24 months will be estimated for each of the treatment groups, including the treatment combinations, using methods described for the primary cost of care endpoint. No formal hypothesis testing will be done, and p-values will be presented for informational purposes only.

Assessment of FI Severity. General linear modeling will be used to analyze change from baseline to 3 months in FI severity as assessed by the Fecal Incontinence Severity Scale (FISS). Independent variables in the model will include randomized treatment group, clinical site, and sex. Missing outcomes will be assumed missing at random for the purpose of this analysis, but sensitivity analyses will be conducted to test the robustness of the results to this assumption. The model will be used to estimate 95% confidence intervals for the change from baseline to 3 months in FISS score in each of the randomized treatment groups. In addition, longitudinal general linear modeling will be used to analyze change from baseline to 6, 12, and 24 months in FISS score. In addition to the independent variables used in the 3-month analysis, the model will include fixed effects for time and the interaction between treatment and time. The model will account for the lack of independence between multiple measures assessed over time on the same study participant by modeling the within-participant covariance structure. For the 6- to 24-month time points, 95% confidence intervals for change from baseline in FISS score will be estimated for responders in each randomized treatment group, as determined at 3 months, and separate estimates will be produced for groups of non-responders who select into each treatment combination. In this analysis, no formal hypothesis testing will be done, and confidence intervals will be compared descriptively.

*Fifty Percent Responder Rate.* The proportion of participants who have at least a 50% reduction in FI episodes will be modeled using the same methods described for the primary efficacy outcome. However, no formal hypothesis testing will be done, and p-values will be presented for informational purposes only. This will be analyzed for each follow-up assessment through 24 months.

*Continence Rate.* The proportion of participants who are continent at each follow up time point will be modeled using the same methods described for the primary efficacy outcome. No formal hypothesis testing will be done, and p-values will be presented for informational purposes only. This will be analyzed for each follow-up assessment through 24 months.

Assessment of Disease-Specific Quality of Life. Change from baseline to 3 months, and to 6 through 24 months in the FI Quality of Life (FIQOL) scale will be analyzed using methods described for the analysis of FI severity.

Assessment of Anxiety, Depression, and Self-Efficacy for Managing Symptoms. Change from baseline to 3 months, and to 6 through 24 months in these Patient Reported Outcomes Measurement Information System (PROMIS) scales will be analyzed using methods described for assessment of FI severity.

